2.2 Analysis sets

2.2.1 Analysis set definition

Safety set (SS) will include all patients who received at least one dose of open-label study drug during this open-label study.

All safety and efficacy analyses will be performed on the safety analysis set and for the total population (not broken down by treatment) unless otherwise specified.

The protocol deviation codes leading to exclusion from the analysis sets defined above are presented in [Table 1-3](#).

Table 1-3 Subject classification rules

Analysis set	PDev Codes that cause subject to be excluded	Non-PDev criteria that cause a subject to be excluded
Safety set	NA	No treatment taken

Note: Protocol Deviation (PDev) Codes are available from the study Data Review Plan (DRP).

Protocol deviations will be summarized by deviation category for the Safety set. The deviation categories defined in the DRP for the study are presented below:

- SELECTION CRITERIA NOT MET
- PROHIBITED CONCOMITANT MEDICATION
- TREATMENT DEVIATION
- OTHER

No major deviation will be defined in this study.

2.2.2 Subgroup of interest

Core study response status at week 20 subgroup

The following e-Diary analyses will be summarized by response status achieved at week 20 of the core study;

- achievement of UAS7=0 response, Hives Severity Score (HSS7) = 0 response and Itch Severity Score (ISS7) = 0 response,
- UAS7, HSS7 and ISS7 summary statistics.

Japanese population

Japanese population will correspond to patients screened in Japan. The following selected safety and efficacy endpoints will be evaluated using the Japanese subgroup population:

Table 1-4 Subgroup analyses for Japanese population

Endpoint/analysis
Safety
Demography table
Disposition table
Baseline characteristic table
Duration of exposure table
Efficacy
Change from baseline in UAS7
Response rate in UAS7=0
Sustained remission (i.e. Achievement of UAS7 ≤ 6)

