6.4.1.1.3 Weekly Urticaria Activity Score (UAS7)

The UAS7 is the sum of the HSS7 score and the ISS7 score. The possible range of the weekly UAS7 score is 0 - 42. Complete UAS7 response is defined as $UAS7 = 0$. Clinical remission is defined as $UAS7 \leq 6$, and the status of “remission” and “sustained remission” will be assessed during treatment and post-treatment epoch, respectively. Clinical relapse is defined as $UAS7 \geq 12$.

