1.2.2 Secondary objectives

The secondary objective of this study is to assess the long-term efficacy of QGE031 in adult CSU patients who completed the CQGE031C2201 study by evaluation of:

- Sustained remission defined as maintaining $UAS7 \leq 6$ over 48 weeks post-treatment follow up epoch among the subjects achieving remission at the end of treatment epoch.

2 Statistical methods

The planned analysis is described in Section 9 (Data Analysis) of the study protocol which is available in Appendix 16.1.1 of the CSR.

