2.6 Analysis of the secondary objectives

Secondary efficacy variables will be summarized by visit with descriptive statistics, which include absolute and relative frequencies for categorical variables and arithmetic mean, standard deviation, minimum, maximum, median and first and third quartile for continuous variables. Time to event variables will be summarized using Kaplan-Meier estimates. Time to event variables that are only analyzed during the treatment epoch will be cut-off at Week 52, otherwise all data available will be included in the analysis (no cut-off at Week 100).

Table 1-6 Secondary efficacy variables

Domain	Variable	Analyzed in treatment epoch	Analyzed in follow-up epoch
Clinical symptoms: total	Complete UAS7 response (UAS7 = 0)	Y	Y
	Achievement of UAS7 <= 6	Y	Y
	Change from Baseline in Urticaria Activity Score (UAS7)	Y	Y
	Time to achievement of complete UAS7 response for patients without response at extension study baseline	Y	N

Domain	Variable	Analyzed in treatment epoch	Analyzed in follow-up epoch
	Time to loss of complete UAS7 response for patients having achieved complete UAS7 response in E1 treatment period at Week 52	N	Y
			
	Time to UAS7 > 6 for patients having achieved UAS7 ≤ 6 in E1 treatment period at Week 52	N	Y
Clinical symptoms: hives	Complete hives response (HSS7 = 0)	Y	Y
	Change from Baseline in HSS7	Y	Y
	Time to achievement of complete hives response for patients without response at extension study baseline	Y	N
	Time to loss of complete hives response for patients having achieved complete hives response in E1 treatment period at Week 52	N	Y
Clinical symptoms: itch	Complete itch response (ISS7 = 0)	Y	Y
	Change from Baseline in Itch Severity Score (ISS7)	Y	Y
			

Note: Y: yes, N: no

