2.6.3 The weekly Urticaria Activity Score (UAS7)

[figure not shown]
The UAS7 is the sum of the HSS7 score and the ISS7 score. The weekly UAS7 score will then range from 0 to 42. Complete UAS7 response is defined as $UAS7 = 0$.

[figure not shown]
Changes from baseline in UAS7 score will be computed and will be summarized along with the absolute values at each visit. Mean with 95% confidence interval will be displayed graphically over time to describe the score change during the study. In addition, UAS7 descriptive statistics will be summarized, [REDACTED].

[figure not shown]
UAS7=0 response will be summarized and plotted by visit and response rate with the 95% Clopper-Pearson exact confidence interval will be included in the analysis. In addition, achievement of UAS7 ≤ 6 will be summarized similarly. Also, UAS7=0 response will be summarized, [REDACTED].

Kaplan-Meier estimates of the time to first UAS7=0 response and of the time to first loss of response for patients having achieved response at Week 52, will be plotted and will be tabulated at defined time points. In addition, Kaplan-Meier estimates of the time to first UAS7 > 6 for patients having achieved UAS7 ≤ 6 at Week 52 [REDACTED], will be tabulated at defined time points.

For patients with concomitant use of omalizumab, UAS scores will be censored at the date of start of omalizumab and treated as missing onward.

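### SAP Table 1-4 defines sustained remission for the Japanese subgroup as by-visit UAS7 ≤ 6, against the stated secondary objective; for the total population no visible text names the estimate.

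*SAP*

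**What the plan says.** Sustained remission is the only secondary objective stated. Protocol 2.2 and SAP 1.2.2 give it the same definition: UAS7 ≤ 6 maintained "over 48 weeks post-treatment follow up epoch among the subjects achieving remission at the end of treatment epoch". Protocol 6.4.1.1.3 sets remission at UAS7 ≤ 6 and says that remission and sustained remission "will be assessed during treatment and post-treatment epoch, respectively".

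In the visible SAP the term appears in two places, SAP 1.2.2 and Table 1-4. Table 1-4 is introduced by "The following selected safety and efficacy endpoints will be evaluated using the Japanese subgroup population", and its last row reads "Sustained remission (i.e. Achievement of UAS7 ≤ 6".

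For the total population, SAP Table 1-6 has two rows on this threshold, and neither is called sustained remission:
- "Achievement of UAS7 <= 6", analysed in both epochs. SAP 2.6.3 describes a by-visit rate with Clopper-Pearson interval for UAS7 = 0 and then says that "achievement of UAS7 ≤ 6 will be summarized similarly".
- "Time to UAS7 > 6 for patients having achieved UAS7 ≤ 6 in E1 treatment period at Week 52", analysed in follow-up only, by Kaplan-Meier to the first UAS7 > 6 and tabulated at time points that the visible text does not list.

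SAP 2.6.10 divides response rates by all patients in the group analysed and counts missing weeks as non-response. In the time-to-loss analyses it leaves out patients without response at Week 52 and censors at the last weekly score or at omalizumab start. The visible part of SAP section 4 announces no change to this endpoint.

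**The concern.** The row in Table 1-4 is written as a definition, and its wording matches the by-visit row of Table 1-6. A by-visit state has no condition on Week 52 and none on maintenance. A programmer who follows Table 1-4 would produce, under the title of sustained remission, a rate with the wrong responders and the wrong denominator. Table 1-4 is also the only visible place that ties the term to an analysis, and it does not list the Kaplan-Meier analysis for the Japanese subgroup. That subgroup would therefore have no visible planned result that answers the secondary objective.

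The total population has a milder gap. A suitable analysis is planned, but the reader is not told that it is the answer to the objective, nor at which time point to read it.

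**Working it through.** The plan states no remission rate, so there is no figure to reproduce. The check is a comparison of definitions, followed by an illustration under assumed rates.

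**1. Definitions side by side**

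| | Objective (SAP 1.2.2, Protocol 2.2) | Table 1-4 gloss (with 2.6.3, 2.6.10) | Kaplan-Meier row (Table 1-6, 2.6.3, 2.6.10) |
|---|---|---|---|
| Denominator | End-of-treatment remitters | All patients in the group analysed | Week 52 remitters |
| Must be in remission at Week 52 | Yes | No | Yes |
| Must stay at UAS7 ≤ 6 | Yes, 48 weeks | No | Yes; the first UAS7 > 6 is the event |
| Dropout, omalizumab start | Not stated | Non-response | Censored |

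**2. Two hypothetical patients**
- UAS7 of 4 at Week 52, 20 at Week 70, 5 at Week 100: counted at Week 100 under the gloss, not sustained under the objective, an event in the Kaplan-Meier analysis.
- Not in remission at Week 52, UAS7 of 5 at Week 100: counted under the gloss, outside the denominator under the objective and in the Kaplan-Meier analysis.

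**3. Illustration.** All rates are assumptions; none comes from the documents. Results are shares because the size of the Japanese subgroup is not given. Let r be the share in remission at Week 52, l the weekly probability of loss and g the weekly probability of regain, over 100 − 52 = 48 weeks with no missing data. Take r = 0.50, l = 0.03, g = 0.01.
- Sustained among remitters: (1 − l)^48 = 0.97^48 = 23.2%. As a share of all patients: 0.50 × 23.2% = 11.6%.
- Long-run share in remission: g/(l + g) = 0.25. Decay factor: (1 − l − g)^48 = 0.96^48 = 0.141.
- Week 52 remitters at UAS7 ≤ 6 at Week 100: 0.25 + 0.75 × 0.141 = 35.6%.
- Week 52 non-remitters at UAS7 ≤ 6 at Week 100: 0.25 × (1 − 0.141) = 21.5%.
- By-visit rate at Week 100, all patients: 0.50 × 35.6% + 0.50 × 21.5% = 28.5%.
- Make-up of the 28.5%: 11.6% sustained, 6.2% relapsed and regained, 10.7% not in remission at Week 52. So (6.2 + 10.7)/28.5 = 59% of those counted would not meet the definition.

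**4. Sensitivity to regain (r and l as above)**

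| Weekly regain | UAS7 ≤ 6 at Week 100, all patients | Sustained, of Week 52 remitters |
|---|---|---|
| 0% | 11.6% | 23.2% |
| 1% | 28.5% | 23.2% |
| 3% | 50.0% | 23.2% |

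With no regain the same patients are counted and only the denominator differs, so the by-visit rate is the lower one. With regain it can be the higher one. Across r = 30–70%, l = 1–5% and g = 0–3%, the by-visit rate runs from 2.6% to 74.3% of all patients and the sustained rate from 8.5% to 61.7% of remitters.

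**5. Kaplan-Meier.** Without censoring, the estimate at 48 weeks in this model is 0.97^48 = 23.2%, equal to the proportion in the objective.

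**The case against.** The strongest reply is that this is loose wording in one row of a subgroup table. The SAP keeps the protocol definition unchanged in 1.2.2, and Protocol 6.4.1.1.3 uses the one threshold for both terms and separates them by epoch, so the gloss may be shorthand for the cut-off. The main analysis includes the Kaplan-Meier row, in which neither misclassification can occur. The plan is descriptive and tests no hypothesis (SAP 2.5.5).

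Much of this stands. A reader might infer that the SAP replaces sustained remission by a point-in-time rate for the whole trial. The documents do not support that: the explicit gloss is in Table 1-4 only, and Table 1-6 never attaches the term to the by-visit row. A reader might also infer that no per-patient rate is planned anywhere. That cannot be claimed either, because parts of Table 1-6, of 2.6.3 and of section 4 are redacted and 2.6.4 to 2.6.9 are not visible.

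Nor is censoring in the Kaplan-Meier analysis an error. Censoring dropouts or counting them as failures is a choice of estimand, and SAP 2.6.10 states a rule for each type of analysis. A patient who leaves after a relapse as defined in Protocol 5.6.1 (UAS7 ≥ 12) has already passed 6 and is an event, provided the weekly score was recorded.

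The shorthand reading explains the row but does not repair it. The visible text gives no other instruction for the Japanese figure, and the row as written conflicts with SAP 1.2.2 whatever the redacted text contains.

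**Conclusion.** The point holds for the Japanese subgroup: Table 1-4 contradicts the SAP's own objective, and following it gives a wrongly defined sustained-remission figure. For the total population the finding is smaller. The Kaplan-Meier analysis among Week 52 remitters tracks the definition, but no visible text names it as the estimate, and no visible row gives the proportion.

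The size cannot be derived from the documents, which give neither remission, loss or regain rates nor the number of Japanese patients. The figures above rest on assumed constant weekly rates and complete data. They show only that the two quantities can differ widely and in either direction. No hypothesis test is affected; what is at stake is the correct reporting of the only secondary objective.

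**What to change.** 1. In Table 1-4, replace the gloss with the SAP 1.2.2 definition and add the time to UAS7 > 6 among Week 52 remitters for the Japanese subgroup.
2. In Table 1-6 and 2.6.3, name the Kaplan-Meier estimate at 48 weeks of follow-up (Week 100) among Week 52 remitters as the sustained-remission estimate. The time point needs stating because SAP 2.6 applies no cut-off at Week 100.
3. Beside it, report n/N among Week 52 remitters with a Clopper-Pearson interval, overall and for the Japanese subgroup. Count early discontinuation and omalizumab start as not sustained, in line with the response-rate rule in 2.6.10, and state how weeks with insufficient diary data are handled. This supplements the Kaplan-Meier estimate and does not replace it. SAP 2.6.10 reports 17 patients on omalizumab after treatment; how many were Week 52 remitters is not stated.
4. Keep the by-visit UAS7 ≤ 6 rate under its own name.

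The cost is wording and one table from data already collected. The n/N figure may be less favourable than the Kaplan-Meier estimate, since it counts as failures patients whom the latter censors.

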2.3 Patient disposition, demographics and other baseline characteristics

2.3.1 Patient disposition

The number of screened subjects who complete the treatment epoch in study CQGE031C2201 and complete at least Visit 203 (Week 32 of the follow-up epoch, ≥ 16

weeks after last injection) and present with active disease as defined by $UAS7 \geq 12$ will be included in the Open label Treatment period.

The number and percentage of subjects in the SS who completed/discontinued the full 52-week treatment epoch, and the reason for discontinuation will be presented. The number and percentage of subjects in the SS who entered/completed/discontinued the follow-up epoch, and the reason for discontinuation during the follow-up epoch will also be presented. Patient disposition during the treatment and follow-up epochs will be listed.

A separate duration of study follow-up report will be created. Duration of follow-up in weeks will be calculated as $(\text{the date of the follow-up epoch end date} - \text{the date of the follow-up epoch start date} + 1) / 7$.

2.3.2 Demographic and baseline characteristics

Demographic information will be summarized based on the Safety Set population.

The following demographic information will be reported from CQGE031C2201 core study baseline:

- Sex (Male, Female)
- Race (White, Black or African American, Asian, American Indian or Alaska Native, Unknown, Other)
- Ethnicity (Hispanic or Latino, East Asian, South Asian, Russian, Mixed ethnicity, Unknown, Other)
- Height (cm)

And the rest of the below mentioned demographic information will be reported from extension study baseline information:

- Age (years) (derived using date of first extension study dose)
- Age group (< 65, >= 65 years)
- Weight (kg)
- Body Mass Index (BMI) – calculated as $\text{weight (kg)} / (\text{height (m)})^2$
- BMI group (< 25, 25 - < 30, >= 30 kg/m^2)

Summary statistics will also be provided for demographics and baseline characteristics for Japanese population.

Baseline characteristics will also be summarized based on the Safety Set population.

The following baseline information will be reported from core study baseline data:

- Randomization strata (background medication)
- Positive Chronic Urticaria (CU) test (i.e. test result > 10): Yes or No
- Weekly urticaria activity score
- Weekly itch severity score
- Weekly hives severity score
- Duration of CSU (years)

■ [REDACTED]

The following baseline characteristics information will be reported from extension study baseline information.

And the following baseline characteristics information will be reported from extension study baseline (over 7 days prior to extension treatment start) data.

- Weekly itch severity score
- Weekly hives severity score
- Weekly UAS

2.3.3 Medical history

Any condition entered on the *Medical history* CRF will be coded using the Medical Dictionary for Regulatory Activities (MedDRA) dictionary version 20.1 or later. Listings will be provided for the overall medical histories including listings of; cardiovascular history, urticaria related history, malignancy medical history and other relevant medical history.

Listings will be based on the Safety set.

2.4 Treatments (study treatment, rescue medication, concomitant therapies, compliance)

2.4.1 Study treatment / compliance

Patients will receive two subcutaneous injections every 4 weeks at 13 visits during the open label treatment epoch (i.e. at Day 1, Week 4, Week 8, Week 12 to Week 48).

Compliance is assured as study drug needs to be administered by study personnel every 4 weeks via subcutaneous injection. Administration of study drug, date, time and injection site will be recorded in the source documents and on the Drug Administration Record eCRF for each injection.

The analysis of study treatment data will be based on the Safety set.

The duration of exposure to study treatment in weeks will be summarized by Safety set. Duration of exposure is defined as the date of the last treatment minus the date of first extension study drug administration plus 4 weeks (28 days).

2.4.2 Prior and concomitant therapies

Prior and concomitant medication / surgery and medical procedures

Prior medications are defined as treatment taken and stopped prior to first dose of the core study drug. Prior medications were reported and analyzed in the core study and will not be reported in the extension study.

Listings will be provided for the medications and for the significant surgeries and medical procedures which were ongoing at the end of the core study or started after the end of the core study, and ended prior to first dose of the extension study drug.

Concomitant medications are defined as any medication given at least once after the first day of first extension study drug dose, and will be summarized on the safety set.

In case of missing end date the medication will be considered as concomitant. If it is partially missing, then the medication month and year will be compared to the month and year of the

first injection date, to know if the medication stopped prior to the drug or not. In case of uncertainty the medication will be considered as concomitant.

Medications will be identified using the Novartis Drug and Therapy Dictionary (NovDTD) including the Anatomical Therapeutic Chemical (ATC) code. Medications will be presented in alphabetical order, by ATC code.

Concomitant medications for CSU starting or continuing during the treatment epoch or during the follow-up epoch will be summarized for each epoch, by type of therapy, ATC code, preferred term and symptom treated. Non-urticaria related concomitant medications starting or continuing during the treatment epoch or during the follow-up epoch will be summarized for each epoch, by ATC code and preferred term.

Concomitant significant surgeries and medical procedures starting or continuing during the treatment epoch or during the follow-up epoch will be summarized for each epoch, by primary system organ class and MedDRA preferred term.

Concomitant use of rescue medication

Concomitant use of rescue medication (using eCRF information) starting during the treatment epoch or during the follow-up epoch will be summarized for each epoch, by ATC code and preferred term.

The number of tablets of rescue medication used over the past 24 hours to control conditions such as itch or hives is recorded once daily in the eDiary by the patient. The total weekly number of tablets of rescue medication from the e-Diary data will be summarized by study week. Median with quartiles will be displayed graphically over time to describe the score change during the study. The total weekly number of tablets of rescue medication will be calculated as the sum of the number of tablets per day, over 7 days.

If rescue medication use was not recorded (due to not completing the eDiary entry) on one or more days over the week, then the total weekly number of tablets will be missing.

Concomitant use of omalizumab

The use of omalizumab is allowed during study, concomitant use of omalizumab (using eCRF information) starting during the treatment epoch or during the follow-up epoch will be listed.

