5.5.6 Rescue medication

Fexofenadine, loratadine, and cetirizine (H1-AH), in addition to being used as background medication will be allowed as rescue medication and used on an as needed basis during treatment and follow-up epochs. The selection of any one rescue medication should be made once for an individual patient. A switch of the rescue medication for an individual patient or between the core and extension study is not permitted. The patients will use the rescue medication at the indicated dose. If required for symptomatic relief, patients may take up to 4x the approved dose of the rescue medication, depending on local clinical practice and guideline. H1-AH rescue medication will be sourced locally.

As an additional safety precaution for the treatment of anaphylactic reactions, patients will be supplied with epinephrine, either via an auto-injector (if available) or as per other local standard of care. The investigator will train the patients on how to detect such reactions and how to use epinephrine. After any use of epinephrine, patients will need to seek immediate medical attention to ensure that the initial reaction has been successfully controlled and/or to trigger additional therapeutic steps.

The use of epinephrine will be recorded on the concomitant medication CRF page.

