7.1 Adverse Events

An adverse event (AE) is any untoward medical occurrence (i.e., any unfavorable and unintended sign [including abnormal laboratory findings], symptom or disease) in a patient or clinical investigation patient after providing written informed consent for participation in the study. Therefore, an AE may or may not be temporally or causally associated with the use of an investigational product.

For all patients who have signed informed consent and are entered into the next epoch (Extension 1 Treatment epoch) of the study, all adverse events occurring after informed consent is signed will be recorded on the Adverse Event CRF.

The occurrence of adverse events should be sought by non-directive questioning of the patient at each visit during the study. Adverse events also may be detected when they are volunteered by the patient during or between visits or through physical examination, laboratory test, or other assessments.

Abnormal laboratory values or test results constitute adverse events only if they fulfill at least one of the following criteria:

- they induce clinical signs or symptoms,
- they are considered clinically significant,
- they require therapy.

Clinically significant abnormal laboratory values or test results should be identified through a review of values outside of normal ranges/clinically notable ranges, significant changes from baseline or the previous visit, or values which are considered to be non-typical in patient with underlying disease. Investigators have the responsibility for managing the safety of individual patient and identifying adverse events. Alert ranges for labs and other test abnormalities are included in [Appendix 1](#) and will be described in the laboratory manual.

Adverse events should be recorded in the Adverse Events CRF under the signs, symptoms or diagnosis associated with them, accompanied by the following information:

- the severity grade
 - mild: usually transient in nature and generally not interfering with normal activities
 - moderate: sufficiently discomforting to interfere with normal activities
 - severe: prevents normal activities
- its relationship to the investigational treatment (no/yes), or
- its duration (start and end dates) or if the event is ongoing an outcome of not recovered/not resolved should be reported.
- whether it constitutes a SAE (see [Section 7.2.1](#) for definition of SAE)
- action taken regarding investigational treatment.

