2.5.1 Adverse events

All adverse events which start after the first dose of study medication in the extension study and within 16 weeks of last dose, or events present prior to the first dose of extension study treatment

and increased in severity (within 16 weeks of last dose), will be considered as a treatment emergent adverse events. Treatment emergent adverse events (TEAEs) will be presented overall (including those that started during treatment and follow-up epoch) and those which started during the treatment epoch. Non-TEAEs will be presented for those which started during the follow-up epoch.

Adverse events that started during the core study were reported and analyzed in the core study and will not be included in tables of the extension study unless they become more severe. They will, however, be included in listings with additional collected information (e.g., outcome) as applicable.

Adverse events that started in the core study but became more severe in the extension study will be reported and analyzed as new events.

Treatment emergent adverse events with the number and percentage of patients having any adverse event by system organ class (SOC) and preferred term (PT) will be provided for:

- All adverse events
- Adverse events by maximum severity
- Adverse events suspected by the investigator as study drug-related
- Serious adverse events
- Adverse events leading to permanent discontinuation of study drug (only for treatment epoch)

Also, a separate summary table for most frequently reported TEAEs during the study, by SOC and PT, will be produced. Most frequent TEAEs will be those with their PT representing at least 5% of subjects.

Clinicaltrials.gov and EudraCT

For the legal requirements of ClinicalTrials.gov and EudraCT, two required tables on <on-treatment/treatment emergent> adverse events which are not serious adverse events with an incidence greater than 5% and on <on-treatment/treatment emergent> serious adverse events and SAE suspected to be related to study treatment, will be provided by system organ class and preferred term on the safety set population.

If for a same patient, several consecutive AEs (irrespective of study treatment causality, seriousness and severity) occurred with the same SOC and PT:

- a single occurrence will be counted if there is ≤ 1 day gap between the end date of the preceding AE and the start date of the consecutive AE

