2. If the AE start date year value is less than the treatment start date year value, the AE started before treatment. Therefore:
 - a. If AE month is missing, the imputed AE start date is set to the mid-year point (01JulYYYY).
 - b. Else if AE month is not missing, the imputed AE start date is set to the mid-month point (15MONYYYY).

3. If the AE start date year value is greater than the treatment start date year value, the AE started after treatment. Therefore:
 - a. If the AE month is missing, the imputed AE start date is set to the year start point (01JanYYYY).
 - b. Else if the AE month is not missing, the imputed AE start date is set to the later of (month start point (01MONYYYY), AE start reference date + 1 day).
4. If the AE start date year value is equal to the treatment start date year value:
 - a. And the AE month is missing the imputed AE start date is set to the AE reference start date + 1 day.
 - b. Else if the AE month is less than the treatment start month, the imputed AE start date is set to the mid-month point (15MONYYYY).
 - c. Else if the AE month is equal to the treatment start date month or greater than the treatment start date month, the imputed AE start date is set to the later of (month start point (01MONYYYY), AE start reference date + 1 day).

If complete (imputed) AE end date is available and the imputed AE start date is greater than the (imputed) AE end date, then imputed AE start date should be set to the (imputed) AE end date.

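### A non-rescue medication last given on the first extension dosing day falls between the SAP's two medication outputs, and adverse events dated that day need a stated treatment-emergence rule

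*SAP*

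**What the plan says.** **Medications.** SAP 2.4.2 plans two general outputs. One is a listing of medications that were ongoing at the end of the core study or started after it, "and ended prior to first dose of the extension study drug". The other is a summary on the Safety Set, with this definition: "Concomitant medications are defined as any medication given at least once after the first day of first extension study drug dose". A missing end date makes a medication concomitant. A partial end date is compared by month and year with the first injection, and: "In case of uncertainty the medication will be considered as concomitant".

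The same section plans three further outputs that do not use the concomitant definition:
- a table of rescue medication from the eCRF, selected by a start within the epoch;
- weekly rescue tablets from the eDiary;
- a listing of omalizumab started in either epoch.

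On epinephrine, Protocol 5.5.6 says: "The use of epinephrine will be recorded on the concomitant medication CRF page".

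**Adverse events.** SAP 2.5.1 defines treatment-emergent events with this opening: "All adverse events which start after the first dose of study medication in the extension study". Protocol 7.1 asks for the start and end dates of each event and names no clock time. SAP 2.4.1 says that the time of each injection is recorded.

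**The concern.** The first rule closes before the first dose, and the second opens only after the first dosing day. Day 1 lies between them.

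Day 1 matters in this study. Protocol 3.6 names hypersensitivity, including anaphylaxis, and injection-site reactions among the reported events. Protocol 5.5.4 keeps patients on site for 2 hours after each of the first three doses. Epinephrine goes on the concomitant medication page, so whether it is reported depends on this definition. Protocol 5.6.2 lists emergency epinephrine for an anaphylactic or anaphylactoid reaction among the reasons to stop study treatment. For such a patient, no later study dose can give rise to a use that enters the table.

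The plan also does not say how an event with a complete start date equal to the dose date is classed. Safety is the primary objective, and the general adverse event tables are built on treatment-emergent status.

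**Working it through.** The plan gives no figure for this point, so the check is to apply the rules to cases. Inputs are the SAP 2.4.2 rules and SAP 2.1.2 (Day 1 is the first extension dose; there is no Day 0). Dates are taken as complete unless marked.

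| Case | Ended before first dose? | Given after Day 1? | Own separate output? | Output as written | Output after the fix |
|---|---|---|---|---|---|
| Epinephrine, Day 1 only | No | No | No | None | Concomitant summary |
| Corticosteroid, Day 1 only | No | No | No | None | Concomitant summary |
| Drug from Day -5 to Day 1 | No* | No | No | None | Concomitant summary |
| H1-antihistamine rescue, Day 1 only | No | No | Rescue table, eDiary Week 1 | Covered | Covered |
| Drug from Day -5 to Day -2 | Yes | No | No | Pre-dose listing | Pre-dose listing |
| Drug from Day 1 to Day 2 | No | Yes | No | Concomitant summary | Concomitant summary |
| End date missing | Not known | By default | No | Concomitant summary | Concomitant summary |

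*If the last use on Day 1 was known to precede the injection, the listing rule could be met. The medication date rules in SAP 5.1.3 work in days, months and years only, so this cannot be assumed.

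The uncovered interval is one calendar day. It falls to zero when the cut-off becomes on or after the date of first dose.

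**Which cases escape.** eDiary Week 1 is Days 1 to 7 (SAP Table 1-2), so rescue tablets on Day 1 are counted there. Omalizumab started on Day 1 would be listed. Epinephrine is different. It appears under the rescue heading in Protocol 5.5.6 but is recorded on the concomitant medication page, while SAP 5.1.3 refers to a separate rescue medication page.

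**Adverse events.** Four passages bear on a complete Day 1 date.
1. SAP 2.5.1 requires a start after the first dose, not after the first day.
2. SAP 2.1.4 has a same-day rule, which assumes an untimed assessment came before the dose. It covers baseline assessments, not events.
3. SAP 5.1.2 places most partial start dates in or after the treatment start month at least one day after the reference date. It does not address complete dates.
4. SAP 2.5.1 presents events that are not treatment-emergent only for the follow-up epoch. A Day 1 event classed that way would enter no general event table.

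**Scale.** The documents give no first-dose reaction rate. Purely to show a range, take the incidences on the axis of Figure 9-1 (Protocol 9.7) as an assumed first-day rate p, with N = 240. The expected number is 240 × p, and the chance of at least one case is 1 − (1 − p)^240.
- p = 0.1%: 0.24 expected; chance 21%
- p = 1%: 2.4 expected; chance 91%
- p = 5%: 12 expected; chance above 99.9%

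These are reactions, not treated reactions. They also leave out unrelated drugs that happened to stop on Day 1.

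**The case against.** The intent is visible in SAP 2.4.2 itself. The partial-date rule asks whether a medication stopped before the study drug, which is a two-way split, and the table sentences select by starting or continuing in the epoch. A sensible programmer might include Day 1 anyway. That stands as evidence of intent, but it does not close the gap. The epoch wording subdivides concomitant medications as already defined, and that definition excludes Day 1. The result is also perverse: an incomplete end date in the month of the first dose is counted, while a complete Day 1 date is not.

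Three stronger readings are tempting, and the documents do not support them.

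- *All Day 1 medication is missing from every output.* Rescue, eDiary tablets, omalizumab and uncertain dates are covered, as shown above.
- *First-dose reactions themselves would disappear.* SAP 2.5.1.1 summarizes and lists events of special interest, including hypersensitivity and injection-site reactions, with no stated limit to treatment-emergent events. SAP 2.5.1.2 lists all adjudicated hypersensitivity reactions and uses treatment emergence only as a flag. SAP 2.3.1 tabulates treatment discontinuations with reasons.
- *The day-after imputation shows that a Day 1 onset is excluded.* It applies to partial dates only. Under SAP 5.1.2 an event that ends on the extension start date can be given the extension reference date, and the final rule then caps its imputed onset at the end date, which is Day 1.

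On the wording of SAP 2.5.1, a reaction during post-injection observation does start after the dose and qualifies. It would be lost only if the comparison were programmed as a date later than the dose date, which nothing in the plan instructs. The absence of an event time is inferred from Protocol 7.1, because the CRF is not shown.

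The likely number is small. Only 1 of 13 dosing days is affected, and many entrants already received QGE031 in the core study. Protocol 3.6 reports one anaphylaxis case by July 2015 and about 390 exposed by January 2015. As a rough scale, 240 ÷ 390 ≈ 0.6 cases over all doses, with unequal cut-off dates and the dose number not stated.

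**Conclusion.** The medication gap is real as written. A non-rescue medication with a complete last-use date of Day 1 falls in neither the pre-dose listing nor the concomitant summary, contrary to the section's own split by whether the drug stopped before study treatment. The record is still collected (Protocol 5.5.7), so what is lost is the reporting, not the data.

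For adverse events the finding is weaker. There is no same-day rule, so the treatment-emergent count or flag of a Day 1 event depends on programming. The events of most interest would still be listed.

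The size is one calendar day per patient and an unknown, probably small, number of patients. An assumed rate such as 1 to 2% (2.4 to 4.8 of 240 patients) has no basis in the documents and should not be quoted as an estimate. The analysis is descriptive, so no test, power or sample size changes. The conclusion rests on a literal reading of SAP 2.4.2 and on medication being recorded by date.

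**What to change.** **SAP 2.4.2.** Define concomitant medication as any medication given at least once on or after the date of first extension dose, that is, with an end date on or after that date or ongoing. Word the pre-dose listing by date as well (end date before that date), so that the two groups meet without a gap or overlap. Keep the default for missing and uncertain dates.

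**SAP 2.5.1 (secondary).** State that an adverse event with a complete start date equal to the date of first extension dose is treatment-emergent unless the record documents onset before the injection. Use the same wording in SAP 4, where the definition is repeated.

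**Cost.** Two sentences and a comparison operator in the programs, with no new data collection. The downside is that a few medications or events from before the injection on Day 1 may be counted, which errs on the cautious side for a safety study.
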